6.2 Examination Procedures

The following ophthalmic examinations will be conducted in the surgery eye (study eye) at intervals specified in Table 1, The Schedule of Assessments. The fellow eye (non-study eye) may be examined at the investigators' discretion.

- **Best Corrected Visual Acuity (BCVA):** BCVA will be measured at every visit except Visit 2 (Surgery; Day 0). The Early Treatment Diabetic Retinopathy (ETDRS) log of the minimum angle of resolution (logMAR) will be used to measure BCVA.
- **Intraocular Pressure (IOP):** IOP will be measured at every visit except Visit 2 (Surgery; Day 0) in mmHg using an applanation tonometer.
- **Ophthalmoscopy:** Ophthalmoscopy will be performed at Visit 1 (Day -14 to Day -2) and Visit 5 (Day 15) by a board-certified ophthalmologist.
- **Biomicroscopy:** Slit lamp biomicroscopy, including the evaluation of ACC and anterior chamber flare (ACF), chemosis, bulbar conjunctival injection, ciliary injection, corneal edema, and keratic precipitates will be conducted by a board-certified ophthalmologist at every visit except Visit 2 (Surgery; Day 0).
- **Visual Analog Scale (VAS):** Eye pain/discomfort and photophobia will be evaluated at every visit except Visit 2 (Surgery; Day 0) using a Visual Analog Scale (VAS), scoring from 0 to 100 using a mark on a 100 mm line (0 = absent; 100 = maximum).
- **Pain assessment via diary (Pain Diary):** Surgery eye pain will be evaluated prior to each IP dose using a pain scale included in the pain and dosing diary that subjects complete at home.

7.0 EVALUATION, RECORDING AND REPORTING OF ADVERSE EVENTS

All AEs either observed by the investigator or study site staff or reported by the subject spontaneously or in response to a direct question regarding the subject's health by the investigator will be recorded in the source document and AE eCRF.

Events reported before signing the consent form should be recorded as medical history; once the ICF is signed new conditions or worsening of existing conditions or episodes that increase in frequency should be recorded as AEs in the source document and AE eCRF.

To standardize the collection of AEs during a study, subjects should be asked a standard question to elicit AEs: "Have you had any problems since your last visit or telephone call?" and "What is the status of [list previously reported unresolved AEs]?" Subjects will also be instructed to contact the investigator immediately if they note any unusual systemic or ocular AEs between visits.

Throughout the course of the study, the investigator must remain alert to possible adverse experiences or untoward findings. If adverse experiences occur, the first concern will be the safety of the subject. Appropriate medical intervention will be provided by the investigator.

The collection, review and management of safety data (AEs and SAEs) will be conducted in compliance with the requirements of the FDA as well as the local IRB/Independent Ethics Committee (IEC).

7.1 Definitions

Adverse Event

An AE is any untoward medical occurrence associated with the use of an IP in humans, whether or not considered related to the IP.

An AE can therefore be any unfavorable and unintended sign (including an abnormal laboratory finding, for example), symptom, or disease temporally associated with the use of an IP, without any judgment about causality. An AE can arise from any use of the IP (e.g., off-label use, use in combination with another drug) and from any route of administration, formulation or dose, including overdose.

Medical conditions or diseases present before a subject starts study treatment are only considered AEs if they worsen after the subject signs informed consent.

Diagnostic and therapeutic non-invasive and invasive procedures, such as surgery, should not be reported as AEs. However, the medical condition for which the procedure was performed should be reported if it meets the definition of an AE. For example, an acute appendicitis that begins during the AE-reporting period should be reported as the AE and the resulting appendectomy noted according to the eCRF completion guideline.

Adverse Event Reporting Period

The AE reporting period for this study begins upon signing the consent form and ends at the completion of the subjects' final visit exam. All AEs that occur in study subjects during the AE-reporting period must be reported in the source documents and on the AE eCRF, whether or not the event is considered related to the IP. In addition, any known untoward event that occurs subsequent to the AE reporting period that the investigator assesses as possibly related to the IP should be recorded in the source documents and reported to the sponsor or designee.

Serious Adverse Event (SAE)

An SAE is an event that, in the view of either the investigator or sponsor, results in any of the following outcomes:

- death
- a life-threatening AE or sight-threatening AE, where ophthalmics are involved
- inpatient hospitalization or prolongation of existing hospitalization
- a persistent or significant incapacity or substantial disruption of the ability to conduct normal life functions
- a congenital anomaly/birth defect

- an important medical event that may not result in death, be life-threatening/sight-threatening, or require hospitalization may be considered serious when, based upon appropriate medical judgment, they may jeopardize the subject and may require medical or surgical intervention to prevent one of the outcomes listed above. Examples of such events are intensive treatment in emergency room or at home for allergic bronchospasm; blood dyscrasias or convulsions that do not result in hospitalization; or development of drug dependency or drug abuse.

The criterion of inpatient hospitalization is met if the subject is admitted to the hospital as the result of an AE, even if the subject is released on the same day. An emergency room visit does not qualify as “inpatient hospitalization” unless the subject is admitted to the hospital during the visit; however, the reason for the emergency room visit may qualify as an SAE based on another SAE criteria (e.g., life threatening or medically significant event).

Pre-existing Conditions

In this study, a pre-existing condition is a disorder/disease present before the AE-reporting period starts (i.e., prior to the subject signing the ICF) and noted on the Medical History eCRF. A pre-existing condition should not be reported as an AE unless the condition worsens or episodes increase in frequency during the AE-reporting period.

7.2 Adverse Events Associated with Study Procedures

Visual Acuity

A worsening of BCVA of 3 lines or more in logMAR score should be captured in the source documents and the appropriate AE eCRF.

IOP

An increase in IOP of ≥ 10 mmHg from Visit 1 or any subsequent visit should be captured as an AE in the source documents and on the AE eCRF.

Biomicroscopy

Anterior chamber cell (ACC) and ACF, chemosis, bulbar conjunctival injection, ciliary injection, corneal edema, and keratic precipitates will be assessed in the study. Since the severity of these assessments will be recorded and carefully monitored during the study, worsenings do not need to be recorded as AEs unless the investigator judges it appropriate. Any treatment emergent findings (findings that were not present prior to dosing with IP, or a worsening relative to baseline [before IP dosing]) outside of these assessments should be recorded as an AE.

Ophthalmoscopy

A new finding or a significant worsening (2 units or more) from baseline should be recorded as an AE.

VAS

Pain/discomfort and photophobia will be assessed in the study eye. Since the severity of these assessments will be recorded and carefully monitored during the study, worsenings do not need to be recorded as AEs unless the investigator judges it appropriate.

7.3 Reporting and Evaluation of AEs and SAEs

Table 2 presents the reporting guidelines for AEs and SAEs. It is important that the investigator comply with the SAE reporting timelines in order to assure that safety reporting timelines of IRB/IEC and regulatory authorities such as the FDA can be met.

Table 2: Requirements for Reporting Adverse Events and Serious Adverse Events to Sponsor

Type	Reporting Time	Type of Report
Serious	Within 24 hours	Adverse Event Report (AE eCRF) Serious Adverse Event Report Form
Non-serious	Per eCRF submission procedure	Adverse Event Report (AE eCRF)

All information relevant to the SAE must be recorded on the appropriate SAE Report Form, and the form submitted immediately (within 24 hours of learning of the event) to the sponsor Medical Monitor or designee:

The investigator must also provide sponsor or designee a copy of all pertinent medical records such as source documents, hospitalization records, death certificates etc. that are de-identified and contain only the study subject number and the subject initials. The investigator should maintain a copy of these medical records in his/her files, as well as any information and medical judgments from colleagues or other medical personnel who assisted in the treatment and follow-up of the subject.

The investigator should ensure that the subject receives appropriate medical treatment and follow-up. Subjects should receive follow-up until the SAE resolves or resolves with sequelae (as judged by the investigator).

Institutional Review Board or Independent Ethics Committee

The investigator will inform the IRB/IEC of any SAE/serious, unexpected, suspected adverse reaction according to the IRB/IEC's specific reporting guidelines.

For all serious, unexpected, suspected adverse reactions, the sponsor or designee will provide documentation to the investigator for the investigator's report to the IRB/IEC or local regulatory authorities.

The investigator must provide documentation of all such IRB/IEC notifications to the sponsor or designee. Copies of each report must be kept in the investigator's files.

7.4 Follow-up of Adverse Events and Serious Adverse Events

All AEs, regardless of severity, will be followed throughout the study to the final study visit, until they resolve or resolve with sequelae (as judged by the investigator).

At the final study visit, new AEs, as well as follow-up information for continuing AEs, will be recorded in the eCRF and source document. Non-serious ongoing AEs will be followed beyond the final study visit at the discretion of the investigator and recorded in the source documents.

If an SAE is unresolved at the final study visit, it will be followed by the investigator until it resolves or resolves with sequelae (as judged by the investigator). Follow-up data for such SAEs will be recorded in the source document and reported to the sponsor or designee.

Subjects withdrawn from the study due to an AE or SAE will be followed by the investigator until the outcome is determined (resolved or resolved with sequelae) and, where appropriate, additional written reports and documentation will be provided to the sponsor.

8.0 STATISTICAL ASSESSMENTS

8.1 Primary Efficacy Endpoint

The primary efficacy endpoint is the proportion of subjects with an ACC grade of 0 at Day 15.

Anterior Chamber Cells	
Grade*	Cell Count
0	0
1	1-5
1	6-10
2	11-20
3	21-50
4	> 50

*Grade 1 includes cell count 1-5 and cell count 6-10.

8.2 Secondary Efficacy Endpoint

The secondary efficacy endpoints are the proportion of subjects who achieve a pain score of 0 on the visual analog scale (VAS) (0-100 mm scale) for each post-surgical assessment at Days 1, 8, 15, 18, and 29.

8.3 Safety Endpoints

- Incidence of ocular adverse events and serious adverse events
- Incidence of non-ocular adverse events and serious adverse events
- Measurement/evaluation and change from baseline in the study eye at each scheduled visit for the following ocular-specific parameters:
 - BCVA
 - IOP

- Slit-lamp biomicroscopy
- Ophthalmoscopy findings
- Photophobia

## **1.0 INTRODUCTION**

The purpose of this Statistical Analysis Plan (SAP) is to provide detailed descriptions of the statistical methods, data derivations and data displays for study protocol C-16-305-003 “A PHASE 3, RANDOMIZED, MULTICENTER, DOUBLE-MASKED STUDY TO COMPARE THE OCULAR SAFETY, TOLERABILITY, AND EFFICACY OF ISV-305 (0.1% DEXAMETHASONE IN DURASITE® 2) TO DURASITE 2 VEHICLE FOR THE TREATMENT OF INFLAMMATION AND PAIN ASSOCIATED WITH CATARACT SURGERY” dated 31st May 2017 for final analysis. The table of contents and templates for the tables, figures, and listings (TFLs) will be produced in a separate document.

Any deviations from this SAP will be described and justified in the Clinical Study Report (CSR). The preparation of this SAP has been based on International Conference on Harmonisation (ICH) E3 and E9.

All data analyses and generation of TFLs will be performed using Statistical Analysis System (SAS®) 9.4 or higher version.

## **2.0 STUDY OBJECTIVES**

To evaluate the ocular safety, tolerability, and efficacy of topical administration of ISV-305 (0.1% dexamethasone in DuraSite 2 ophthalmic suspension) compared with DuraSite 2 Vehicle when dosed BID for 1 day prior to surgery, the day of surgery, and 14 days post cataract surgery.

## **3.0 STUDY DESIGN**

### **3.1 General Study Design**

This study is a Phase 3, randomized, multicenter, double-masked, vehicle-controlled, parallel group clinical trial, with total study duration of 29 days, consisting of 3 phases:

- Screening/Randomization Phase (~2 weeks, Visit 1, Days -14 to -2)
- Dosing Phase (~2 weeks, Phone call Visit to Visit 4, Days -1 to 14)
- Evaluation Phase (~2 weeks, Visit 5 to Visit 7, Days 15 to 29)

Prior to enrollment, the study will be discussed with prospective subjects and those wishing to enter will be asked to give written informed consent. For subjects who, according to local regulations, have not yet reached the age of majority, the subject’s parent(s) or legally authorized representative must sign the Informed Consent Form (ICF) and the minor’s written assent will be obtained according to the local requirements.

Subjects  $\geq 17$  years of age scheduled to undergo uncomplicated unilateral cataract surgery and who meet all inclusion and none of the exclusion criteria will be randomized in a 2:1 ratio: 160 in the ISV- 305 group and 80 in the vehicle group. Subjects will be enrolled at approximately 15 study centers in the US.

### **3.2 Randomization and Masking**

In this double-masked trial, subject randomization is managed in accordance with InSite Vision’s Standard Operating Procedure (SOP). The randomization is generated by a statistician that is not

affiliated with the study. Once the randomization plan is generated it is provided to the Head of Quality Assurance (QA) only.

The central randomization plan contains the coded treatment assignments for each randomization number. The randomization plan is shared with Manufacturing to allow for proper packaging and labeling of study supplies. Once the packaging of the IP is complete and the product released, all records are sealed and secured in a locked area of Document Control. The randomization plan remains under the confidential control of the InSite Vision QA Department or designee until the study is completed.

Eligible subjects will be randomly assigned to the ISV-305 and vehicle groups in a 2:1 ratio according to the central randomization plan. At each site, subjects will be randomized sequentially to the appropriate treatment group by assigning the number corresponding to the lowest numbered drug kit available at the site.

In this double-masked (blinded) study, the study site, the study subjects (including caregiver), and sponsor/designee (other than as stated above) are masked to the identity of the IP. Dosing will be performed by the subject or caregiver, and not by study site personnel.

Unmasking of the randomization code prior to study completion due to a medical emergency or suspected AE is also managed in accordance with InSite Vision's SOP.

The randomization is not unmasked until the study is complete and the database is locked.

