2.0 STUDY DESIGN

This study is a Phase 3, randomized, multicenter, double-masked, vehicle-controlled, parallel-group clinical trial. Approximately 240 subjects will participate in the study and will be randomized in a 2:1 ratio to the ISV-305 group (160 subjects) and the vehicle group (80 subjects).

Written informed consent will be obtained from all subjects prior to any study-specific procedure. Subjects will be enrolled into a 16-day dosing phase, followed by a 2-week evaluation phase. There will be 7 visits scheduled during the study: a screening visit between 2 and 14 days prior to surgery; 3 visits during the dosing phase (Day 0 [Surgery Day], Day 1, and Day 8); and 3 visits during the evaluation phase (Day 15, Day 18, and Day 29). In addition, there will be a telephone call on Day -3 to remind subjects to begin dosing on Day -1, the day before surgery. Subjects will instill 3 doses prior to surgery (2 doses on Day -1, and 1 dose on Day 0 prior to surgery), 1 dose in the evening after surgery and continue dosing BID for 14 days after surgery.

Subjects will be randomized and receive instructions for dosing at home and completing a pain and dosing diary. Subjects will be cautioned to dose only for the specified amount of time. One bottle of investigational product (IP) will be dispensed to the subject, and a second bottle will remain at the site as a precaution only in the event of loss, etc., and will not be dispensed unless necessary. Throughout this protocol, the surgery eye is referred to as the study eye, and the fellow eye is referred to as the non-study eye.

All ratings and procedures should be performed by the same examiner from visit to visit whenever possible. Additional exams may be scheduled as necessary to ensure the safety of the subjects during the study period.

Subjects who terminate use of IP for any reason will be withdrawn from the study, the reason(s) clearly described on the subject's electronic Case Report Form (eCRF) and source documents, and the sponsor or designee will be notified.

If the investigator determines lack of efficacy during the dosing period, administration of a rescue medication (i.e., another medication to treat ocular inflammation and/or ocular pain in the surgery eye [study eye]) must occur after subject is withdrawn from the study, and be clearly documented on the source documents and the designated eCRF.

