### **7.4.2 Analysis of Primary Efficacy Endpoint**

The primary efficacy endpoint is the proportion of subjects with an ACC grade of 0 at Day 15.

The difference between treatment groups will be tested using a two-sided Z-Test with continuity correction and pooled variance using the mITT population. A subject with an ACC grade of 0 at the Day 15 visit or the last assessment prior to the Day 15 visit (in the event that Day 15 was not completed) will be considered a responder to therapy. If a subject has an ACC score of >0 at Day 15 or the last assessment prior to the Day 15 visit (in the event that Day 15 was not completed), that subject will be considered a failure (or non-responder) in the primary efficacy endpoint analysis. Additionally, any subject receiving a rescue medication between Day 0 and the Day 15 visit (inclusive) will be considered a treatment failure.

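### The primary test ignores site in a trial of about 15 centres and adds a continuity correction: it is valid but conservative, and a site-stratified CMH test without the correction has more power

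*SAP*

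**What the plan says.** - **Size and sites.** Protocol 2.0: "Approximately 240 subjects will participate in the study". SAP 3.1: subjects "will be randomized in a 2:1 ratio: 160 in the ISV- 305 group and 80 in the vehicle group", and "Subjects will be enrolled at approximately 15 study centers in the US". The text supplied gives no assumed response rates, target power or site sizes.
- **Allocation.** SAP 3.2 describes one list: "The central randomization plan contains the coded treatment assignments for each randomization number". Kits are taken in order at each site, "by assigning the number corresponding to the lowest numbered drug kit available at the site". The section does not say whether the list is blocked or stratified by site.
- **Grading.** Protocol 6.2 has a board-certified ophthalmologist grade anterior chamber cells at the slit lamp. Protocol 2.0 adds: "All ratings and procedures should be performed by the same examiner from visit to visit whenever possible". No central reading is described.
- **Test.** SAP 7.4.2: "The difference between treatment groups will be tested using a two-sided Z-Test with continuity correction and pooled variance using the mITT population". SAP 7.4.1.1 says the same for cells in general, and SAP 7.4.3 uses the same test for VAS pain. None of these sections contains a site term, a site-stratified sensitivity analysis or a treatment-by-site check.

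**The concern.** The endpoint is the strict cut between no cells and any cells. It is probably judged by a local examiner after local surgery, so response rates may well differ between sites. Cells and pain at entry cannot be used for adjustment, because exclusion criterion m removes anyone who has either. Site is an obvious prognostic factor that is known for everyone.

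A pooled test leaves between-site variation in the noise. If kits are also balanced within site, the pooled variance is larger than the true variance of the difference and the test runs below its nominal level. The continuity correction lowers the level further, whether or not sites differ.

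What is at stake is efficiency. Under SAP 7.4.1.2 the five pain tests are carried out only if the primary null hypothesis is rejected, so a narrow miss on cells loses every secondary claim as well.

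**Working it through.** **Inputs from the documents:** 160 and 80 subjects, about 15 sites, two-sided 0.05, pooled variance, continuity correction (CC). The allocation agrees with itself (160 + 80 = 240; 160/80 = 2). The figure of 240 cannot be reproduced, because no response rates or power are given.

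**Assumptions:** vehicle/active response of 10/25%, 20/38% and 30/50%; equal sites (15 × 16) or skewed sites (50 down to 2); blocks of 3 within site, blocks of 6 within site, or no balance within site; normal site effect on the logit with SD 0, 0.25, 0.5, 1 or 1.5; common treatment odds ratio; no dropout. For scale, around a typical site rate of 20% (logit −1.386), sites one SD either side have rates of about 13% and 29% if the SD is 0.5, and about 8% and 40% if it is 1.

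**Step 1: the correction alone, by formula.** The planned statistic is z = (|d| − ½k) / √(p(1−p)k), with k = 1/160 + 1/80 = 0.01875, so ½k = 0.009375.

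- Null, 20% in both arms: SE = √(0.16 × 0.01875) = 0.0548. The correction is worth 0.009375/0.0548 = 0.171, so the critical value is in effect 1.960 + 0.171 = 2.131 and the level is 3.3%.
- Null, 30% in both arms: SE = √(0.21 × 0.01875) = 0.0627, shift 0.149, level 3.5%.
- Power at 20 vs 38%: pooled p = (16 + 60.8)/240 = 0.32; null SE = √(0.2176 × 0.01875) = 0.0639; alternative SE = √(0.38 × 0.62/160 + 0.20 × 0.80/80) = 0.0589. Without CC: Φ((0.18 − 1.96 × 0.0639)/0.0589) = 82.4%. With CC: Φ((0.170625 − 1.96 × 0.0639)/0.0589) = 78.0%. The correction costs about 4.4 points with no site effect at all.

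**Step 2: simulation, 40,000 trials per case** (Monte Carlo error about 0.2 points). Power (%) at 20 vs 38% with equal sites:

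| Balance within site | Site SD | Planned Z, CC | Z, no CC | CMH, CC | CMH, no CC |
|---|---|---|---|---|---|
| Blocks of 3 | 0 | 78.3 | 82.5 | 78.0 | 82.4 |
| Blocks of 3 | 0.5 | 78.6 | 82.8 | 79.7 | 83.9 |
| Blocks of 3 | 1 | 80.0 | 84.3 | 84.3 | 88.2 |
| None | 0 | 78.6 | 82.8 | 75.8 | 80.5 |
| None | 1 | 78.6 | 82.7 | 81.9 | 86.2 |

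The SD 0 rows agree with Step 1.

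**Step 3: separate the two changes.**

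- Blocks of 3, SD 1: dropping CC gives 84.3 − 80.0 = +4.3; stratifying then gives 88.2 − 84.3 = +3.9; total +8.2.
- No balance, SD 0: dropping CC gives 82.8 − 78.6 = +4.2; stratifying then gives 80.5 − 82.8 = −2.3; total +1.9.

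Over all 90 cases (3 rate pairs × 2 site patterns × 3 allocation schemes × 5 SDs), CMH without CC minus the planned test ranged from +0.7 to +12.1 points. The effect of stratifying alone, both tests without CC, was:

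| Site SD | Change in power (points) |
|---|---|
| 0 | −2.4 to −0.1 |
| 0.25 | −1.9 to +0.2 |
| 0.5, blocked within site | +0.4 to +1.1 |
| 0.5, not blocked | −0.9 to −0.2 |
| 1 | +1.8 to +4.2 |
| 1.5 | +5.3 to +8.0 |

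With CC in both tests the pattern is the same, and the largest loss at SD 0 is 3.4 points.

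**Step 4: level.** With 20% or 30% response in both arms, the planned test rejected in 1.6% to 3.6% of trials and CMH without CC in 4.8% to 5.1%. The Z-test without CC fell below 5% through site variation only when allocation was balanced within site (2.5% to 3.0% with blocks of 3 and SD 1.5). Without balance it stayed near 5% at every SD.

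**The case against.** The strongest objection is that the comparison changes two things at once. Much of the gain over the planned test comes from dropping the continuity correction, which has nothing to do with site. Like for like, stratifying lost power in all 18 cases with no site effect and in most with SD 0.25. This stands, and it is why the two effects are reported separately. A reader might infer that stratifying by site always gains power; the calculations do not support that.

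A reader might also infer from the kit rule that allocation is balanced within site. SAP 3.2 does not say so: it describes how kits are drawn from a central list and refers to an operating procedure that is not in the documents. Both possibilities were therefore run.

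Third, a prespecified conservative test is a choice, not an error, since 5% is an upper bound that the planned test respects. This also stands. Nothing here shows an inflated error rate, or that 240 subjects are too few.

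Three narrower objections also hold. Site is not the only usable baseline factor: age, IOP and BCVA are available from Visit 1. Local grading is a fair inference rather than a stated fact, and the same-examiner sentence is a preference. The pain endpoint and its Hochberg procedure were not simulated, and the examiner argument does not carry over to a scale that subjects rate themselves.

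None of this removes the main result: against the test actually written in the SAP, the stratified test without correction was ahead in every case, at a valid level.

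**Conclusion.** The point holds as a loss of efficiency, not of validity. The planned primary test runs at about 2% to 4% instead of 5%. CMH by site without correction gained about 1 to 12 points of power over it in every simulated case while keeping its level near 5%. About 3 to 6 of those points come from the correction alone. Stratifying adds about 2 to 8 more if site rates differ clearly (logit SD 1 or more). It starts to pay at an SD of about 0.5 if kits are balanced within site, and at about 1 if they are not. If sites do not differ and kits are not balanced within site, it costs up to about 2.4 points against an uncorrected Z-test.

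These sizes rest on assumed response rates, site sizes, blocking and site variation, with no dropout and a common odds ratio. The direction against the planned test did not depend on which of the simulated values was used. The change is worth making, but keeping the planned test would not invalidate the trial.

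**What to change.** Before unmasking:

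1. In SAP 7.4.1.1 and 7.4.2, make the primary test a CMH test stratified by site, without continuity correction.
2. Fix a rule for pooling small sites, based on enrolment counts only, since a site with subjects in one arm contributes nothing to CMH.
3. Report a Mantel-Haenszel risk difference with 95% CI. SAP 7.4.2 names no interval for the primary endpoint.
4. In SAP 3.2, state whether the kit list is blocked by site.
5. In SAP 7.4.3, use the same method for pain for consistency, noting that the gain there has not been simulated.

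If the sponsor keeps the Z-test, prespecify the stratified analysis as a sensitivity analysis and decide on the continuity correction as a separate question.

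The cost is SAP wording and a pooling rule. The statistical downside is a small power loss against an uncorrected Z-test if sites do not differ; in the cases simulated there was none against the planned test.
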